### 10.1. Summary of Pharmacokinetic Sampling and Sample Properties

The serum PK of a single dose of EV68-228-N will be assessed from serial blood samples collected approximately 15 minutes prior to infusion, at end of infusion (within a  $\pm$  5-minute window), at 1-, 3-, and 5-hours post end of infusion (within a  $\pm$  15-minute window), at 24- and 48-hours after the end of the infusion (within  $\pm$  3-hour window), and at 7, 14, 28, 60, 90, and 121 days after the end of the infusion (within  $\pm$  1-, 2-, 3-, 7-, 14-, and 14-day window, respectively). EV68-228-N will be quantified by a validated ECL assay.

Individual concentration-time plots will be generated, and outliers will be identified as values greater or less than 3 SDs from the mean within each Dose Cohort and time point. Outliers will not be excluded from summary statistics but will be excluded from the NCA and will be discussed in the CSR.

Samples with bioanalytical errors or quality issues reported by the laboratory will be excluded. Collection times of samples missing the actual collection time will be imputed using the nominal collection time. Such samples will be identified in the analysis report ([Listing 25](#)).

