#### **4.3.1.4. Participant Replacement**

Participants who withdraw, or are withdrawn from this study, or are lost to follow-up after signing the informed consent form (ICF) and receiving an infusion will not be replaced. Participants who withdraw, or are withdrawn from this study, or are lost to follow-up after signing the ICF but before infusion may be replaced.

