#### **4.4.3. Method of Assigning Participants to Dose Cohorts (Randomization)**

Enrollment/randomization will be performed through the enrollment module in the electronic data capture system, maintained by the Statistical and Data Coordinating Center (SDCC). Eligible participants in three dose escalating cohorts will be randomized in a 5:1 ratio to receive either EV68-228-N or placebo. The randomization is based on a variable blocked scheme to provide an approximately balanced allocation to the Dose Cohorts during the study.

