## 5. SAMPLE SIZE CONSIDERATIONS

As a Phase 1, first-in-human study, the number of participants was chosen principally on feasibility and using a 5:1 randomization scheme. Thus, three cohorts of 10 participants each (n=30) and 6 placebo recipients (total N=36) are proposed. With 10 participants in each cohort receiving study product, the chance of observing at least one AE of probability 20% or more is approximately 89.3% (see [Table 3](#)). Therefore, if no AEs of a given type occur in an active dose group, we can be relatively confident that they will occur in fewer than 20% of people once the treatment is implemented.

PK parameters are not a primary outcome of the study, so it has not been powered for this, however with a sample size of 10 participants per dose level, assuming the pharmacokinetics are not dose proportional, a parameter with a coefficient of variation of 120% or less has a 90% chance to be observed within 80% and 120% of the geometric mean.

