#### 6.3.4. Pharmacokinetics Population

The PK population will consist of participants in the Safety Population who have at least one evaluable serum PK sample for the estimation of  $C_{max}$  or  $AUC_{0-\infty}$  and received a full dose. This set will be used to assess the

---

PK endpoints. Any participants or data values excluded from this analysis set will be identified, along with their reason for exclusion. Participants receiving placebo are excluded from PK analysis.

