#### **6.5. Missing Data**

All attempts will be made to collect all data per protocol. As missing data are expected to be minimal, no imputation will be performed for missing values. Any data point that appears to be erroneous or inexplicable based on clinical judgment will be investigated as a possible outlier.

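### The 3-SD outlier rule for PK concentrations cannot flag any value with 10 or fewer participants per dose, so the outlier exclusion from the NCA can never be triggered

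*SAP*

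**What the plan says.** Section 10.1 sets a numerical outlier rule for serum concentrations: "outliers will be identified as values greater or less than 3 SDs from the mean within each Dose Cohort and time point". It also fixes the consequence: "Outliers will not be excluded from summary statistics but will be excluded from the NCA and will be discussed in the CSR". A separate sentence in the same section handles known assay problems: "Samples with bioanalytical errors or quality issues reported by the laboratory will be excluded".

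Other sections determine how many values fall in each dose-by-time cell:

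- Section 5: "With 10 participants in each cohort receiving study product". Table 1 shows the same 10 active and 2 placebo per cohort.
- Section 6.3.4: "Participants receiving placebo are excluded from PK analysis".
- Section 4.3.1.4: participants who leave after "receiving an infusion will not be replaced".
- Section 10.2.1: apart from two limited imputation rules, concentrations below the quantitation limit are treated as missing.
- Section 4.4.3: the blocked randomization is to give an "approximately balanced allocation to the Dose Cohorts during the study".

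Section 6.5 adds a general check: "Any data point that appears to be erroneous or inexplicable based on clinical judgment will be investigated as a possible outlier". It states no exclusion step.

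**The concern.** With about ten values, an extreme observation inflates the SD against which it is judged. There is a hard ceiling on how many SDs away it can appear, and at n=10 that ceiling is below 3. The rule looks like a safeguard but does nothing.

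This has two consequences. The CSR is to discuss outliers found by this rule, and a report of none would read as the result of a check that could not have found any. And if an implausible concentration does turn up without a laboratory flag, removing it from the NCA would be a decision taken outside the stated rule, after seeing the data. PK is a secondary, unpowered, descriptive objective, but section 2.1 says the safety and PK data will help identify a target dose for later efficacy trials.

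**Working it through.** **Cell size.** The SAP gives no operating figure for the 3-SD rule. Its one figure tied to the group size does reproduce: the chance of at least one event of probability 20% among 10 is 1 - 0.8^10 = 0.893, matching the 89.3% in section 5. So n=10 per dose is the planned maximum. Placebo exclusion, no replacement after infusion and missing BQL values can only keep it there or lower it.

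**Bound.** Let one value deviate from the mean by a. The other n-1 deviations sum to -a, so their squares sum to at least a²/(n-1). The total sum of squares is then at least a²·n/(n-1), the sample SD is at least a·√n/(n-1), and therefore

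a/SD ≤ (n-1)/√n.

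| n | limit, sample SD: (n-1)/√n | limit, population SD: √(n-1) |
|---|---|---|
| 8 | 2.475 | 2.646 |
| 9 | 2.667 | 2.828 |
| 10 | 2.846 | 3.000 |
| 11 | 3.015 | 3.162 |

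At n=10 neither version can exceed 3. The result does not depend on the distribution or on taking logs. Nine values of 100 and one of 1,000,000 give exactly 2.846.

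**Simulation.** In 200,000 log-normal cells of 10 per setting, with one value 3-, 5- or 10-fold too high and CVs from 20% to 120%, the rule flagged nothing. The largest distance seen was 2.846.

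**If allocation gave 11 active.** Let the value lie d SDs from the mean of the other ten, using their SD. Then z² = d²((n-1)/n)² / [(n-2)/(n-1) + d²/n]. Setting z=3 and n=11 gives d² = 8.1/0.0082645 = 980, so d = 31.3.

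**What one undetected error does (illustration; the documents give no error rate).** Take one Cmax among 10 too high by a factor f, with an assumed true CV of 30%.

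- Geometric mean is multiplied by f^(1/10): 3^0.1 = 1.12; 10^0.1 = 1.26.
- Log variance becomes ln(1.09) + (ln f)²/10: 0.0862 + 0.1207 = 0.2069 for f=3; 0.0862 + 0.5302 = 0.6164 for f=10.
- CV = √(exp(s²)-1): about 48% for f=3; about 92% for f=10.

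**Do the λz criteria in section 10.2.2 cover the gap?** They do not act on Cmax or AUC0-48. For terminal errors the answer depends on half-life and on the points used. Take a mono-exponential decline with the last value 3-fold too high:

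| Assumed half-life | adjusted R², 4 points (days 28, 60, 90, 120 after dosing) | adjusted R², 6 points (days 7 to 120) |
|---|---|---|
| 14 d | 0.925 (passes; half-life read as 17.8 d) | 0.968 (passes) |
| 21 d | 0.79 (fails) | 0.918 (passes) |
| 28 d | 0.57 (fails) | 0.835 (fails) |

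The 0.9 threshold catches some such errors and misses others.

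**The case against.** The strongest reply accepts the algebra and disputes the consequence. An inert rule keeps every concentration, including genuine extremes, which is safer than automatic deletion. Laboratory-reported errors are already excluded. Individual plots are drawn, potentially important bioanalytical errors are to be discussed, and section 6.5 calls for implausible values to be investigated. Section 6.3.4 and Listing 25 require a reason for each exclusion, and section 1 requires departures from the SAP to be justified. Concentration summaries are unaffected because outliers stay in them by plan, and the primary safety endpoints are untouched.

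Most of this is fair and limits the severity. It does not rescue the rule. The plots and section 6.5 carry no exclusion criterion. The documentation requirements would make an ad hoc exclusion visible without making it pre-specified.

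No reading of the text escapes the bound. Leave-one-out calculation is not stated, and counting all 12 cohort members conflicts with the placebo exclusion. Eleven active participants is not the plan. If it happened the rule could fire: on the raw scale with a CV of 30%, a 10-fold error lies about (10-1)/0.30 = 30 SDs out, near the 31.3 threshold.

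It is also fair that replacement rules are imperfect. Their detection falls quickly as between-participant variability rises, as shown under the fix.

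**Conclusion.** The rule is wrong as written. At n of 10 or fewer, the chance that it flags any value in any dose-by-time cell is exactly zero. This rests only on the planned 10 active participants per dose and on the plain reading that the mean and SD include the value tested. The effect is confined to the secondary PK parameters. How far they would be distorted depends on an error rate that the documents do not give, so the geometric mean and CV figures are illustrations under an assumed CV of 30%. The plan should be corrected, but the primary safety analysis is not at risk.

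**What to change.** Before unblinding, replace the rule in section 10.1 with one that can act at n=10, and name a single rule. Apply it only to quantifiable post-dose concentrations within Dose Cohort and time point, where at least 8 such values exist; below 8, rely on plot review.

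- **Leave-one-out:** flag if |ln C - mean of the others| > 4 × SD of the others. It raises fewer false flags.
- **MAD:** flag if |ln C - median| > 3.5 × 1.4826 × MAD. It holds up better if two values in one cell are wrong.

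Use a flag as a query trigger. Exclude a flagged value from the NCA only with a documented collection or assay cause. Otherwise keep it and report the affected parameters with and without it.

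The cost is SAP wording, a few lines of code, and some needless queries and second NCA runs. There are 3 doses × 12 post-dose times = 36 cells and 36 × 10 = 360 samples. Simulated in clean log-normal data:

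| | Leave-one-out, 4 SD | MAD, 3.5 |
|---|---|---|
| Values flagged, n=10 | 0.5% (about 2 of 360) | 1.7% (about 6 of 360) |
| Cells with a flag, n=10 | 5% | 12.5% |
| Cells with a flag, n=8 | about 8% | about 14% |

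Chance of flagging a single error at n=10 (leave-one-out / MAD), by assumed CV:

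| Error | CV 30% | CV 50% | CV 120% |
|---|---|---|---|
| 3-fold | 47% / 50% | 14% / 20% | 3% / 5% |
| 5-fold | 87% / 83% | 38% / 42% | 6% / 11% |
| 10-fold | 99.6% / 98% | 76% / 74% | 16% / 22% |

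The 120% column uses the only CV in the SAP (section 5), which is a ceiling in a precision statement and not an expected value. Neither rule finds every error, so plot review should stay.

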### 3.3.4. Pharmacokinetic Parameters

$AUC_{0-\infty}$  is defined as the AUC from the time of dosing extrapolated to time infinity based on the last observed concentration ( $C_{last}$ ) and the elimination rate constant ( $\lambda_z$ ), where  $C_{last}$  is defined as the last observed positive concentration above the lower limit of quantitation (LLOQ) and  $\lambda_z$  is defined as the first-order rate constant associated with the terminal (log-linear) portion of the curve describing the rate of elimination from serum. Estimated by linear regression of time vs. log concentration.  $AUC_{0-\infty}$  will be computed by adding  $AUC_{0-last}$  to an area extrapolated by  $C_{last}$  divided by  $\lambda_z$ , as shown below:

$$AUC_{0-\infty} = AUC_{0-last} + \frac{C_{last}}{\lambda_z}$$

$AUC_{0-last}$  is defined as the AUC from the time of dosing to the time of the last quantifiable concentration above the LLOQ based on observed concentrations.

$AUC_{0-48}$  is defined as the AUC from the time of dosing to the time of the last quantifiable concentration above the LLOQ up to and including the nominal 48 hr time point based on observed concentrations.

Maximum serum concentration ( $C_{max}$ ) is defined as the maximum observed concentration, occurring the time of maximal serum concentration ( $T_{max}$ ), in serum following the first dose of EV68-228-N.

$T_{max}$  is defined as the time at which the maximum observed serum concentration occurs. Because non-steady-state data is collected, the entire curve is considered. If the maximum observed concentration is not unique, then the first maximum is used.

---

The terminal elimination half-life ( $t_{1/2}$ ) is defined as the time it takes serum concentrations to reduce by 50% during the terminal elimination phase and will be estimated by the natural logarithm of 2 ( $\ln(2)$ ) divided by  $\lambda_z$ .

Total serum clearance (CL) is defined as the total clearance and represents a volume that is cleared of the molecule of interest per hour. It will be calculated as the dose divided by the  $AUC_{0-\infty}$ , as shown below:

$$CL = \frac{Dose}{AUC_{0-\infty}}$$

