### 10.2.2. Pharmacokinetic Parameters

PK analyses will be performed using noncompartmental analysis (NCA) using Phoenix WinNonlin version 8.3 or higher (Certara, Radnor, PA).

NCA PK parameters will be calculated using the actual post-dose time. Samples with concentrations greater than the LLOQ will be considered for the estimation of  $\lambda_z$ . Imputing the first BQL concentration following the last concentration greater than LLOQ to LLOQ divided by 2 will be considered on a participant-by-participant basis for participants where the  $\lambda_z$  acceptance criteria are not met by the observed data greater than the LLOQ.  $\lambda_z$  will be computed from the log-transformed concentration data. The correlation between time and concentration at the time points used to estimate  $\lambda_z$  should be sufficiently high (adjusted- $R^2 > 0.9$ ). Additionally, a minimum of three concentrations in the terminal elimination phase will be used for the calculation of  $\lambda_z$ . All concentrations used to calculate  $\lambda_z$  must come from samples taken at or after  $T_{max}$ . The concentrations used to calculate  $\lambda_z$  along with the number of concentrations used for the calculation will be included in the participant serum concentration listing ([Listing 25](#)).

The serum AUC will be computed using the linear-up log-down (linear-log) trapezoidal method.

All serum PK parameters will also be summarized by Dose Cohort using descriptive statistics ([Table 80](#)). Additionally, participant-level PK parameters will be presented by participant in [Table 79](#) in the final report.

The following parameters will be estimated:  $AUC_{0-\infty}$ ,  $AUC_{0-last}$ ,  $AUC_{0-48}$ ,  $C_{max}$ ,  $T_{max}$ ,  $t_{1/2}$ ,  $CL$ , and  $V_z$ .

See Section [3.3.4](#) for parameter definitions.

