**Listing 25: 16.2.9.4: Participant Level Drug Concentrations**

Dose Cohort	Participant ID	Nominal Time Point (hours)	Actual Time pPoint (hours)	Sample Collected Within Time Window	EV68-228-N Concentration (ng/mL)	Used in $\lambda z$ Calculation?	Excluded from PK Analysis	Reason For Exclusion from PK Analysis
3 mg/kg EV68-228-N	XXXXXXX	Pre-Infusion	Pre-Infusion	Yes	0.00	No	No	N/A
	XXXXXXX	0	0.067	Yes	XXXX.XX	No	No	N/A
	XXXXXXX	1	1.2	Yes	XXXX.XX	No	No	N/A
	XXXXXXX	3	2.9	Yes	XXXX.XX	No	No	N/A
	XXXXXXX	5	5.5	No	XXXX.XX	No	No	N/A
	XXXXXXX	24	-	-	XXXX.XX	No	No	N/A
	XXXXXXX	48	51.25	No	XXXX.XX	No	No	N/A
	XXXXXXX	168	180.06	Yes	XXXX.XX	No	No	N/A
	XXXXXXX	336	330.25	Yes	XXXX.XX	No	No	N/A
	XXXXXXX	672	700.5	Yes	XXXX.XX	Yes	No	N/A
	XXXXXXX	1440	1442.1	Yes	XXXX.XX	Yes	No	N/A
	XXXXXXX	2160	2159.33	Yes	BQL*	Yes	No	N/A
	XXXXXXX	2880	2866	Yes	BQL	No	Yes	BQL treated as missing
10 mg/kg EV68-228-N	XXXXXXX	Pre-Infusion	Pre-Infusion	Yes	0	No	No	N/A
30 mg/kg EV68-228-N	XXXXXXX	Pre-Infusion	Pre-Infusion	Yes	0	No	No	N/A

\* Denotes a sample that was reported as BQL but was imputed as LLOQ/2 because it was necessary to compute  $\lambda z$  during the noncompartmental analysis.

Note: Missing actual time points were imputed as the nominal time point for the purpose of analysis.

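### Giving an untimed PK sample its nominal time suits windows of minutes or hours but not the Day 61, 91 and 121 visits, where at worst it shifts one participant's half-life by about -19% to +30%

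*SAP*

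**What the plan says.** SAP section 10.1 sets the rule: "Collection times of samples missing the actual collection time will be imputed using the nominal collection time". It adds that such samples will be identified in Listing 25, whose note reads "Missing actual time points were imputed as the nominal time point for the purpose of analysis". Neither place separates a missing clock time from a missing date, and neither limits the rule to certain visits.

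The same section places the later samples "at 7, 14, 28, 60, 90, and 121 days after the end of the infusion", with a ± "1-, 2-, 3-, 7-, 14-, and 14-day window, respectively". The Day 1 post-infusion draws have windows of 5 or 15 minutes, and the 24- and 48-hour draws ±3 hours.

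Section 10.2.2 states the default: "NCA PK parameters will be calculated using the actual post-dose time". For the terminal slope, section 3.3.4 gives the estimator ("Estimated by linear regression of time vs. log concentration"). Section 10.2.2 says that "a minimum of three concentrations in the terminal elimination phase will be used for the calculation of" λz, and requires adjusted R² above 0.9. The SAP does not bar a sample with an imputed time from the λz fit and plans no sensitivity analysis without it.

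**The concern.** For draws with a window of minutes or hours, the nominal time is close to the true one. At the last three visits the true time may lie 7 or 14 days from the nominal time, and these are the samples that set λz.

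Listing 25 records actual time in hours to two decimals, which cannot be computed without a clock time. Taken literally, a missing clock time alone therefore triggers the nominal value, even if the visit date is on record. The date will usually be recoverable: ADA blood is drawn at the same visits (section 4.1), and Listing 10 reports its actual study day. The rule can thus replace an error of under a day with one of up to 14 days.

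At stake are t1/2 and Vz. Both are named secondary outcomes (section 3.2.2) and are reported per participant in Table 79. The imputed value itself is also not settled, because the last nominal time is given as both 121 and 120 days.

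**Working it through.** The SAP gives no figure on this point, so there is nothing to reproduce. The check asks how far one imputed time can move λz.

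**Inputs from the SAP.** Late nominal times of 60, 90 and 120 days (121 in section 10.1); windows ±7, ±14 and ±14 days; at least three points; adjusted R² > 0.9; t1/2 = ln 2 / λz.

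**Assumptions not in the SAP.** A noise-free mono-exponential terminal phase, with one sample displaced to the edge of its window and analysed at its nominal time. The percentage change in t1/2 does not depend on the true half-life (the same at 10, 21 and 40 days).

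**Three-point fit.** For equally spaced nominal times 60, 90 and 120, the least-squares slope depends only on the two end points:

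λz / λ = (t3 − t1) / 60, with t1 and t3 the true times. If the last sample is displaced by d days, this is (60 + d) / 60.

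- d = +14 (drawn late): 74/60 = 1.233, so t1/2 changes by 60/74 − 1 = -18.9%.
- d = −14 (drawn early): 46/60 = 0.767, so t1/2 changes by 60/46 − 1 = +30.4%.

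For a true t1/2 of 21 days, the estimates are 17.0 and 27.4 days.

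Adjusted R² = 1 − (1 − R²)(n − 1)/(n − 2). With true times 60, 90 and 106, the regression sum of squares (in units of λ²) is 1058 of a total 1090.67, so R² = 0.970 and adjusted R² = 0.940. With 60, 90 and 134 it is 2738 of 2770.67, so R² = 0.988 and adjusted R² = 0.976. Both pass.

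**Other configurations**

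| Points in fit (days) | Displaced sample | Change in t1/2 | Adjusted R² |
|---|---|---|---|
| 60, 90, 120 | last, ±14 d | -18.9% / +30.4% | 0.976 / 0.940 |
| 60, 90, 121 | last, ±14 d | -18.7% / +30.0% | 0.978 / 0.944 |
| 28, 60, 90 | last, ±14 d | -18.3% / +28.8% | 0.976 / 0.942 |
| 60, 90, 120 | first, ±7 d | -10.4% / +13.2% | 0.993 / 0.988 |
| 14, 28, 60 | last, ±7 d | -14.1% / +19.6% | 0.996 / 0.993 |
| 60, 90, 120 | middle, ±14 d | 0% | 0.865 (fails) |
| 28 to 120, four points | last, ±14 d | -12.0% / +15.7% | 0.985 / 0.975 |
| 14 to 120, five points | last, ±14 d | -9.6% / +11.9% | 0.990 / 0.985 |
| 7 to 120, six points | last, ±14 d | -8.4% / +10.1% | 0.992 / 0.989 |

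**Residual noise.** With a 21-day half-life and the three-point fit, the early-drawn case passes adjusted R² > 0.9 in about 71% of simulations at 10% residual CV and 59% at 20%. The late-drawn case passes in about 98% and 84%.

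**Other parameters.** Last sample ±14 days, three-point λz, assumed half-lives of 15 to 28 days:

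- AUC0-∞: +0.9% to +5.3% (early), -0.5% to -3.0% (late).
- CL: -0.9% to -5.0% (early), +0.5% to +3.1% (late).
- Vz: +23.9% to +29.2% (early), -16.4% to -18.5% (late).

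**Cohort summary.** One affected participant in ten shifts the geometric mean t1/2 by 1.304^(1/10) − 1 = +2.7%, or 0.811^(1/10) − 1 = -2.1%.

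**If the recorded date is used.** A timing error of at most 1 day gives 60/61 − 1 = -1.6% to 60/59 − 1 = +1.7%; half a day gives about ±0.8%.

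**Last nominal time.** Section 10.1 gives 121 days. Tables 77-78 give 120 days, and Listing 25 gives 2880 h, which is 2880/24 = 120 days.

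**The case against.** The -19% to +30% range stacks several conditions: a sample with no time, which is the last quantifiable one, drawn at the edge of a ±14-day window, in a fit of exactly three points, with any known date unused. Three is only the SAP's minimum, and more points shrink the error. If the fit were chosen by highest adjusted R² among the last three to six points (a rule the SAP does not state), the noise-free model picks six, and the error is -8.4% to +10.1%. This stands, so the range must be presented as a worst case. It is not contrived, however: the Listing 25 mock-up shows a λz fit on exactly three points (672, 1440 and 2160 h), ending at a ±14-day visit.

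Safeguards also exist. Actual time is the default, section 6.5 expects few missing data, untimed samples are identified in Listing 25, and individual profiles are plotted. The only untimed row in the mock-up is at 24 hours, where the window is ±3 hours. All this makes the problem rarer and visible, but it does not correct the estimate.

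A reader might infer three stronger things that the document does not support:

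- That the SAP orders a recorded date to be thrown away. It says nothing about partly missing date-times; the literal wording merely allows this.
- That the R² requirement never catches the error. A 14-day displacement of the middle point in the 60/90/120 fit fails it, and with noise a good share of early-drawn cases fail too.
- That all parameters derived from λz are equally harmed. AUC0-∞ and CL are not.

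The 120/121-day mismatch is a separate editorial point. It changes the worst case only from +30.4% to +30.0%.

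**Conclusion.** The point holds as a flaw in a stated rule. Applied without limit by visit, nominal-time imputation can move a participant's t1/2 by about -19% to +30% under the worst-case conditions above, and such a fit can still satisfy adjusted R² > 0.9. With four to six points the error is about -12% to +16%; for the ±7-day sample in the 60/90/120 fit it is about -10% to +13%. Vz moves with t1/2, while AUC0-∞ and CL change by a few percent.

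These sizes rest on an assumed mono-exponential terminal phase. The SAP gives no frequency for missing times at late visits, so nothing here shows that the error will occur often. Nor does it threaten the cohort-level description of PK, where one affected participant in ten shifts the geometric mean t1/2 by 2 to 3%. The case for changing the rule is that individual t1/2 and Vz are reported and a better rule costs almost nothing.

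**What to change.** Reword the rule in section 10.1 and the Listing 25 note:

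1. If the collection date is known and only the clock time is missing, use the actual date with another recorded time from that visit, or a fixed default clock time. The SAP defines no planned clock time for Days 8 to 121, so the default must be named. Timing error is then at most about 1 day, and t1/2 error under about 2%.
2. Use the nominal time only where the window is in minutes or hours.
3. If the date of a Day 61, 91 or 121 sample is also unknown, leave it out of the λz fit, or report t1/2 and Vz with and without it.
4. State what happens to an undated Day 8, 15 or 29 sample. In the fits checked, all ending at day 60 or later, displacing one of these to its window edge changed t1/2 by at most 5.1%, so dropping them from the whole noncompartmental analysis is not warranted.

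Separately, reconcile the last nominal time across section 10.1, Tables 77-78 and Listing 25.

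The cost is a few lines of SAP text and one programming rule, with no new data. The downside is in step 3: removing a sample from a three-point fit leaves two, below the SAP's minimum. λz, and with it t1/2, AUC0-∞, CL and Vz, may then occasionally not be estimable for that participant. Reporting with and without the sample avoids losing the estimate altogether.
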